3.8.2. Analysis Windows

Participant visits might not occur on protocol specified days. Therefore, for the purpose of analysis, observations will be assigned to analysis windows.

The analysis windows for HIV-1 RNA, hematology, chemistry, urinalysis, urine pregnancy laboratory tests, eGFR_{CG}, vital signs, and weight are presented in [Table 3-1](#).

[figure not shown]
Table 3-1. Analysis Windows for HIV-1 RNA, Hematology, Chemistry, Urinalysis, Urine Pregnancy Laboratory Tests, eGFR_{CG}, Vital Signs and Weight

Visit ID	Nominal Day	Lower Limit	Upper Limit
Baseline			1
Week 4	28	2	56
Week 12	84	57	126
Week 24	168	127	210
Week 36	252	211	294
Week 48	336	295	378
Week 60	420	379	462
Week 72	504	463	546
Week 84	588	547	630

The analysis windows for CD4+ cell count, CD4 %, and metabolic assessments (including fasting glucose and lipid panel: total cholesterol, high density lipoprotein [HDL], direct low density lipoprotein [LDL], triglycerides, and total cholesterol to HDL ratio are presented in [Table 3-2](#).

Table 3-2. Analysis Windows for CD4+ cell count, CD4 %, and Metabolic Assessments

Visit ID	Nominal Day	Lower Limit	Upper Limit
Baseline	1		1
Week 24	168	2	252
Week 48	336	253	420

The analysis windows for plasma HBV DNA are presented in [Table 3-3](#).

Table 3-3. Analysis Windows for Plasma HBV DNA

Visit ID	Nominal Day	Lower Limit	Upper Limit
Baseline	1		1
Week 24	168	2	252
Week 48	336	253	420

3.8.3. Selection of Data in the Event of Multiple Records in an Analysis Window

Depending on the statistical analysis method, single values are required for each analysis window. For example, change from baseline by visit usually requires a single value, whereas a time to event analysis would not require one value per analysis window. When a single value is needed, the following rule(s) will be used.

If multiple nonmissing numeric observations exist in a window, then records will be chosen as follows:

- For baseline, the latest available record on or prior to the first dose date of study drug will be selected. If there are multiple records with the same time or no time recorded on the same day, average will be used for the baseline value, except for HIV-1 RNA (see below).
- For postbaseline visits:

For CD4+ cell count, CD4%, and HBV DNA, the record(s) collected on the latest day in the window will be selected for analysis.

For other numeric observations (ie, except HIV-1 RNA, CD4+ cell count, CD4%, and HBV DNA), the record(s) collected on the day closest to the nominal day for that visit will be selected. If there are 2 days equidistant from the nominal day, the later day will be selected.

For any numeric observations except HIV-RNA, if there are multiple records on the selected day, the average will be taken.

- For baseline and postbaseline HIV-1 RNA, the latest (considering both date and time) record(s) in the window will be selected. If both “HIV RNA Taqman 2.0” and “HIV RNA Repeat” (ie, the HIV-1 RNA result obtained from an additional aliquot of the original sample) are available with the same collection time, the results from the “HIV RNA Repeat” will be selected for analysis purposes; otherwise, if there are multiple “HIV RNA Taqman 2.0” records with the same collection time, the geometric mean will be taken for analysis purposes.

If multiple valid nonmissing categorical observations exist in a window, records will be chosen as follows:

- For baseline, the last available record on or prior to the first dose date of study drug will be selected. If there are multiple records with the same time or no time recorded on the same day, the value with the lowest severity will be selected.
- For postbaseline visits, the most conservative value within the window will be selected.

4. SUBJECT DISPOSITION

4.1. Subject Enrollment and Disposition

4.1.1. Subject Enrollment

The number and percentage of participants randomized at each investigator site will be summarized by treatment group (B/F/TAF and Delayed Switch to B/F/TAF) and overall using the B/F/TAF safety analysis set. The denominator for this calculation will be the number of participants in the B/F/TAF safety analysis set. Similarly, the number and percentage of participants enrolled in each randomization stratum will be summarized based on reclassified strata using the baseline third agent ARV class based on the Non-Study ARV Medication eCRF.

If there are discrepancies between IWRS and collected data with regard to stratum assignment, a listing of the discrepancies will be provided.

4.1.2. Subject Disposition

The summary of subject disposition will be provided by treatment group (B/F/TAF and Delayed Switch to B/F/TAF) and overall for all screened participants. This summary will include the number of participants screened, screen failure participants who were not randomized, participants who met all eligibility criteria and were not randomized, participants randomized, participants randomized but never treated, participants with delayed switch to B/F/TAF, participants in the B/F/TAF safety analysis set, and the number of participants in the B/F/TAF FAS.

In addition, the number and percentage of the participants in the following categories will be summarized:

- Completed study drug
- Prematurely discontinuing study drug (with summary of reasons for discontinuing study drug)
- Treated in the Extension phase
- Completed study
- Prematurely discontinuing from study (with summary of reasons for discontinuing study).

The denominator for the percentages of participants in each category will be the number of participants in the B/F/TAF safety analysis set.

No inferential statistics will be generated. A data listing of reasons for study drug/study discontinuation will be provided.

4.2. Extent of Study Drug Exposure and Adherence

4.2.1. Duration of Exposure to Study Drug

Duration of exposure will be calculated for the B/F/TAF and Delayed Switch to B/F/TAF groups. Duration of exposure to study drug will be defined as (last dose date - first dose date + 1), regardless of temporary interruptions in study drug administration, and will be expressed in weeks using up to 1 decimal place (eg, 4.5 weeks).

Duration of exposure to study drug will be summarized using descriptive statistics (n, mean, SD, median, Q1, Q3, minimum, and maximum) and as the number and percentage of participants exposed for specified periods, eg, ≥ 4 weeks (28 days), ≥ 8 weeks (56 days), ≥ 12 weeks (84 days), ≥ 24 weeks (168 days), ≥ 36 weeks (252 days), ≥ 48 weeks (336 days), ≥ 60 weeks (420 days), ≥ 72 weeks (504 days).

Summaries will be provided for participants in the B/F/TAF safety analysis set. No inferential statistics will be provided.

4.2.2. Adherence to Study Drug Regimen

Study drug regimen adherence will be computed based on pill counts. The numbers of pills of study drug dispensed and returned are captured on study drug accountability eCRF.

Adherence (%) of study drug regimen will be calculated as follows:

$$\text{Adherence (\%)} = 100 \times \frac{\text{Total No. of pills taken}}{\text{Total No. of pills prescribed}}$$
$$100 \times \frac{\sum \sum \text{No. of pills taken at each dispensing period}^{[1]}}{\sum \sum \text{No. of pills prescribed at each dispensing period}^{[2]}}$$

[1] Number of pills taken at a distinct dispensing period for a study drug is calculated as the minimum of (a) the daily number of pills prescribed for the study drug multiplied by the duration of treatment at the dispensing period, and (b) the number of pills taken for the study drug (number of pills dispensed minus the number of pills returned). Total number of pills taken is determined by summing the number of pills taken for each study drug contained in the study drug regimen from all evaluable dispensing periods.

[2] Number of pills prescribed at a distinct dispensing period for a study drug is calculated as the daily number of pills prescribed for the study drug multiplied by the duration of treatment at the dispensing period. Total number of pills prescribed is determined by summing the number of pills prescribed for each study drug contained in the study drug regimen from all evaluable dispensing periods.

The duration of treatment at a dispensing period for a study drug is calculated as the minimum of (a) the last returned date of study drug at a dispensing period, (b) date of premature discontinuation of the study drug, and (c) next pill dispensing date of the study drug, minus dispensing date of the study drug.

The next pill dispensing date is the following dispensing date of the study drug regardless of the bottle return date.

For a record where the number of pills returned was missing (with “Yes” answered for “Was Bottle returned?” question), it is assumed the number of pills returned was zero. If the number of pills dispensed was missing or any study drug bottle was not returned or the bottle return status was unknown, then all records in that dispensing period for that study drug will be excluded from both denominator and numerator calculation.

Adherence will be calculated using all data from the entire dosing period up to the date of permanent discontinuation of the study drug for participants who prematurely discontinued study drug or completed study drug.

Descriptive statistics for adherence (n, mean, SD, median, Q1, Q3, minimum, and maximum) along with the number and percentage of participants belonging to adherence categories (eg, < 80%, ≥ 80% to < 90%, ≥ 90% to < 95%, ≥ 95%) will be provided for participants who return at least 1 bottle and have calculable adherence during the study in the B/F/TAF safety analysis set. No inferential statistics will be provided.

4.3. Protocol Deviations

A listing will be provided for all participants who violated at least 1 inclusion or exclusion criterion. The listing will include the criteria not met.

Protocol deviations occurring after participants entered the study are documented during routine monitoring. The number and percentage of participants with important protocol deviations by deviation reason and the total number of important protocol deviations by deviation reason (eg, nonadherence to study drug, violation of select inclusion/exclusion criteria) will be summarized by treatment group (B/F/TAF and Delayed Switch to B/F/TAF) for the B/F/TAF FAS. A by-subject listing will be provided for those participants with important protocol deviations.

4.4. Assessment of COVID-19 Impact

This study was ongoing during the novel coronavirus (2019 nCoV [COVID-19]) pandemic which caused a disruption in the regular visit schedules for this study. Some participants were unable to attend onsite visits due to shelter in place guidelines, site closures or other reasons. Visits related to the primary and secondary endpoints of the study were not impacted.

4.4.3. Missed and Virtual Visits due to COVID-19

An overall summary of the number and percentage of participants with missed or virtual visits (e.g., at least 1, with 1, 2, 3 or more visits) due to the COVID-19 pandemic will be provided. The denominator for the percentage calculation will be the total number of participants in the B/F/TAF safety population.

A by-subject listing will be provided presenting participants who missed or had virtual visits due to COVID-19. The determination of missing or virtual visits due to COVID-19 was done using Natural Language Processing (NLP) to search the CRF comment fields. A detailed explanation of the algorithm is given in [Appendix 5](#).

5. BASELINE CHARACTERISTICS

5.1. Demographics and Baseline Characteristics

Subject demographic data (eg, age, sex at birth, gender identity, sexual orientation, race, and ethnicity) and baseline characteristics (eg, body weight, height, and body mass index [BMI]) will be summarized by treatment group (B/F/TAF and Delayed Switch to B/F/TAF) and overall using descriptive statistics (n, mean, SD, median, Q1, Q3, minimum, and maximum) for continuous data and by the number and percentage of participants for categorical data. The summaries of demographic data and baseline subject characteristics will be provided for the B/F/TAF safety analysis set.

5.2. Baseline Disease Characteristics

The following baseline disease characteristics will be summarized by treatment group (B/F/TAF and Delayed Switch to B/F/TAF) and overall using descriptive statistics:

- HIV-1 RNA categories (copies/mL): (a) < 50, (b) ≥ 50
- CD4+ cell count (/μL)
- CD4+ cell count categories (/μL): (a) < 50, (b) ≥ 50 to < 200, (c) ≥ 200 to < 350, (d) ≥ 350 to < 500, and (e) ≥ 500
- CD4 percentage (%)
- Mode of infection (HIV risk factors)
- HIV disease status
- eGFR_{CG} (mL/min)
- HIV/HBV co-infection status (Yes/No/Missing, see Section 8.1 for definition)
- HIV/HCV co-infection status (Yes/No/Missing, see Section 8.2 for definition)
- Duration of HIV Diagnosis (years) (calculated as years prior to year from First Dose/Day 1 date; see programming specifications)
- Duration of HIV Treatment (Years) (calculated as years prior to year from First Dose/Day 1 date; see programming specifications)
- Duration of baseline ARV medication prior to randomization (based on the Non-Study ARV Medication eCRF, see programming specifications)

- Baseline ARV Regimen (based on the Non-Study ARV Medication eCRF, see programming specifications)

Baseline ARV Medication Backbone (FTC+TAF, FTC+TDF, TDF+3TC, ABC+3TC, AZT+3TC)

Baseline 3rd agent (INSTI, NNRTI, PI, CCR5), and further broken down by ingredient

Baseline ARV Medication (Backbone+3rd agent)

5.3. Medical History

General medical history data will be collected at screening and listed only. General medical history data will not be coded.

6. EFFICACY ANALYSES

6.1. Primary Efficacy Endpoint

6.1.1. Definition of the Primary Efficacy Endpoint

The primary efficacy endpoint is the proportion of participants with HIV-1 RNA ≥ 50 copies/mL at Week 24 as determined by the US FDA-defined snapshot algorithm {[U. S. Department of Health and Human Services 2015](#)}.

The analyses of the primary efficacy endpoint were performed in the Week 24 analysis, and will not be repeated here.

6.2. Secondary Efficacy Endpoints

6.2.1. Definition of the Secondary Efficacy Endpoints

The secondary efficacy endpoints include:

- The proportion of participants with HIV-1 RNA ≥ 50 copies/mL at Week 48 as determined by the US FDA-defined snapshot algorithm
- The proportion of participants with HIV-1 RNA < 50 copies/mL at Week 24 and Week 48 as determined by the US FDA-defined snapshot algorithm
- The change from baseline in CD4+ cell count at Week 24 and Week 48

The analyses of the secondary efficacy endpoints were performed in the Week 24 and Week 48 analyses and will not be repeated here.

CCI [REDACTED]
[REDACTED] [REDACTED]
[REDACTED]
[REDACTED]
[REDACTED]
[REDACTED]
[REDACTED]
[REDACTED]
[REDACTED]
[REDACTED]
[REDACTED]
[REDACTED]
[REDACTED]
[REDACTED]
[REDACTED]

CCI [Redacted]

[Redacted]

[Redacted]

[Redacted]

[Redacted]

[Redacted]

[Redacted]

[Redacted]

[Redacted]

[Redacted]

[Redacted]

[Redacted]

[Redacted]

CCI [Redacted]

[Redacted]

[Redacted]

[Redacted]

6.4. Changes from Protocol-Specified Efficacy Analyses

No change from the protocol-specified efficacy analyses are planned.

7. SAFETY ANALYSES

Safety data will be summarized for the participants in the B/F/TAF safety analysis set. All safety data collected up to 30 days after permanent discontinuation of B/F/TAF study will be summarized by treatment group, unless specified otherwise. All safety data will be included in data listings.

7.1. Adverse Events and Deaths

Summaries of AEs by treatment group (B/F/TAF, Delayed Switch to B/F/TAF, All B/F/TAF) will include data collected up to 30 days after permanent discontinuation of study drug.

7.1.1. Adverse Event Dictionary

Clinical and laboratory AEs will be coded using the current version of MedDRA. System organ class (SOC), high-level group term (HLGT), high-level term (HLT), preferred term (PT), and lowest-level term (LLT) will be provided in the AE dataset

7.1.2. Adverse Event Severity

Adverse events are graded by the investigator as Grade 1 (mild), Grade 2 (moderate), Grade 3 (severe) or Grade 4 (life threatening) according to toxicity criteria specified in the protocol. The severity grade of events for which the investigator did not record severity will be left as “missing” for data listings.

7.1.3. Relationship of Adverse Events to Study Drug

Related AEs are those for which the investigator selected “Related” on the AE eCRF to the question of “Related to Study Treatment.” Events for which the investigator did not record relationship to study drug will be considered related to study drug for summary purposes. However, by-subject data listings will show the relationship as missing.

7.1.4. Serious Adverse Events

Serious adverse events (SAEs) will be identified and captured as SAEs if AEs met the definitions of SAE specified in the study protocol. Serious adverse events captured and stored in the clinical database will be reconciled with the SAE database from the Gilead Global Patient Safety (GLPS) Department before data finalization.

7.1.5. Treatment-Emergent Adverse Events

7.1.5.1. Definition of Treatment-Emergent Adverse Events

Treatment-emergent adverse events (TEAEs) are defined as 1 or both of the following:

- Any AEs with an onset date on or after the B/F/TAF study drug start date and no later than 30 days after permanent discontinuation of the B/F/TAF study drug, or
- Any AEs leading to premature discontinuation of B/F/TAF study drug.

7.1.5.2. Incomplete Dates

If the onset date of the AE is incomplete and the AE stop date is not prior to the first dosing date of study drug, then the month and year (or year alone if month is not recorded) of onset determine whether an AE is treatment emergent. The event is considered treatment emergent if both of the following 2 criteria are met:

- The month and year (or year) of the AE onset is the same as or after the month and year (or year) of the first dosing date of study drug, and
- The month and year (or year) of the AE onset is the same as or before the month and year (or year) of the date corresponding to 30 days after the date of the last dose of study drug

An AE with completely missing onset and stop dates, or with the onset date missing and a stop date marked as ongoing or on or after the first dosing date of study drug, will be considered to be treatment emergent. In addition, an AE with the onset date missing and incomplete stop date with the same or later month and year (or year alone if month is not recorded) as the first dosing date of study drug will be considered treatment emergent.

7.1.6. Summaries of Adverse Events and Death

The number and percentage of participants who experienced at least 1 TEAE will be provided and summarized by SOC, HLT, PT, and treatment group (B/F/TAF, Delayed Switch to B/F/TAF, and All B/F/TAF). For other AEs described below, summaries will be provided by SOC, PT, and treatment group (B/F/TAF, Delayed Switch to B/F/TAF, and All B/F/TAF) using the B/F/TAF safety analysis set:

- Any Grade 2, 3, or 4 treatment-emergent AEs
- Any Grade 3 or 4 treatment-emergent AEs
- All treatment-emergent study drug-related AEs
- Any Grade 2, 3, or 4 treatment-emergent study drug-related AEs
- Any Grade 3 or 4 treatment-emergent study drug-related AEs
- All treatment-emergent SAEs
- All treatment-emergent study drug-related SAEs
- All treatment-emergent AEs that caused premature discontinuation from study drug

A brief, high-level summary of AEs described above will be provided by treatment group (B/F/TAF, Delayed Switch to B/F/TAF, and All B/F/TAF) and by the number and percentage of participants who experienced the above AEs. Treatment-emergent deaths observed in the study will be also included in this summary.

Treatment-emergent death refers to deaths that occurred between the first dose date and the last dose date plus 30 days (inclusive).

Multiple events will be counted only once per participant in each summary. Adverse events will be summarized and listed first in alphabetic order of SOC and HLT within each SOC (if applicable), and then by PT in descending order of total frequency within each SOC. For summaries by severity grade, the most severe grade will be used for those AEs that occurred more than once in an individual participant during the study.

In addition to the above summary tables, all treatment-emergent AEs, Grade 3 or 4 treatment-emergent AEs, treatment-emergent study drug-related AEs, Grade 2, 3, or 4 treatment-emergent study drug-related AEs, and treatment-emergent SAEs will be summarized by PT only, in descending order of total frequency.

Summary of treatment-emergent AEs by SOC and PT will also be conducted for all subgroups listed in Section 3.4.2.

By-participant listings will be provided for all AEs, study drug-related AEs, grade 3 and 4 AEs, serious AEs, study drug-related SAEs, and AEs leading to premature study drug discontinuation.

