8.8. Sample Size

Sample sizes of 320 in B/F/TAF FDC and 160 in SBR Group achieve approximately 89% power to detect a non-inferiority margin difference between the group proportions of 0.06 for HIV-1 RNA \geq 50 copies/mL at Week 24. The assumed reference group proportion is 0.04. The treatment group proportion is assumed to be 0.10 under the hypothesis of inferiority. The power is computed for the case when the actual treatment group difference is zero (treatment = reference). The test statistic used is the one-sided Score test (Farrington & Manning) with the significance level of 0.025.

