- v Hepatitis C virus serology will be performed at Screening, Week 48, and Week 72. Participants who are HCVAb positive will have a HCV RNA test performed.
- w Plasma, serum, and urine storage samples will be collected for safety, virology, or PK testing.
- x Collect whole blood sample for participants randomized to SBR only at Week 24.
- y **CCI**
- z Randomization may be performed up to 3 days prior to the in-clinic Day 1 visit provided that all screening procedures have been completed and participant eligibility has been confirmed.
- aa At Week 24, participants randomized to continue their baseline regimen and complete 24 weeks of treatment on their baseline regimen will switch to FDC of B/F/TAF.
- bb FDC of B/F/TAF will be dispensed to Treatment Group 1 only. Study drug accountability will be performed accordingly.
- cc Subjects will receive study drug for dosing until Week 72.

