1.3. Sample Size and Power

A total of 480 HIV-1 infected participants, randomized in a 2:1 ratio to 2 treatment groups, achieves approximately 89% power to detect a noninferiority margin difference between the group proportions of 6% for HIV-1 RNA \geq 50 copies/mL at Week 24.

For sample size and power computation, it is assumed that the reference group proportion is 4%. The treatment group proportion is assumed to be 10% under the hypothesis of inferiority. The power is computed for the case when the actual treatment group difference is zero (treatment – reference). The test statistic used is the one-sided Score test (Farrington & Manning) with the significance level of 0.025. Sample size and power calculations were performed using the statistical software package PASS (Version 14).

In general, a failure rate of 1% to 3% is assumed for switch studies in virologically suppressed participants, and the noninferiority margin for treatment difference is typically set at 4%. The failure rate of 4% and noninferiority margin of 6% used for this study was based on the observation that African Americans have lower rates of virological suppression compared to other cohorts {[DeJesus 2019](#)}. In the United States (US), not all communities have had equitable access to advancements in HIV treatment. African Americans remain disproportionately affected by HIV but have less access to HIV treatment and generally worse health outcomes compared to other racial groups.

Table 1-1 provides approximate power for SBR proportions ranging from 2% to 4% with noninferiority margin ranging from 4% to 6%. A total of 480 HIV-1 infected participants, randomized in a 2:1 ratio to 2 treatment groups, achieves approximately 87% power to detect a noninferiority margin difference between the group proportions of 4%.

Table 1-1. Power for Various Proportions and Noninferiority Margins

SBR Proportion	Noninferiority Margin	Approximate Power	Actual Alpha
4%	6%	91%	0.026
3%	5%	88%	0.026
2%	4%	87%	0.024

SBR N 160; B/F/TAF N 320; alpha targeted at 0.025. The test statistic used is the one sided Score test (Farrington & Manning). Power and actual alpha were computed using binomial enumeration of all possible outcomes.

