3.2. Subject Grouping

Participants will be grouped into the following 3 groups:

- B/F/TAF: this group includes all participants randomized to the B/F/TAF group and who received at least 1 dose of B/F/TAF
- Delayed Switch to B/F/TAF: this group includes all participants randomized to the SBR group who switched to B/F/TAF at Week 24 and received at least 1 dose of B/F/TAF
- All B/F/TAF: all participants who received at least one dose of study assigned B/F/TAF (both immediate and delayed switch to B/F/TAF).

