7.2.2.2. Summaries of Laboratory Abnormalities

The following summaries (number and percentage of participants) for treatment-emergent laboratory abnormalities will be provided by lab test and treatment group (B/F/TAF, Delayed Switch to B/F/TAF, and All B/F/TAF); participants will be categorized according to the most severe postbaseline abnormality grade for a given lab test:

- Treatment-emergent laboratory abnormalities
- Treatment-emergent Grade 3 and 4 laboratory abnormalities

For all summaries of laboratory abnormalities, the denominator is the number of participants with any nonmissing postbaseline values for the particular laboratory test.

A by-subject listing of all treatment-emergent laboratory abnormalities and treatment-emergent Grade 3 or 4 laboratory abnormalities will be provided by subject ID number and visit in chronological order.

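### The final safety tables show side by side, and pool, crude percentages from groups whose planned B/F/TAF exposure differs by 24 weeks, with no exposure-adjusted rate or common-window incidence table.

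*SAP*

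**What the plan says.** The immediate-switch group starts B/F/TAF on Day 1. The other group stays on its baseline regimen and starts at Week 24 if it completes those 24 weeks (SAP 1.2, Figure 1-1 notes). Main treatment ends at study Week 48 for both. An optional extension adds up to 24 weeks, and the footnote to Protocol Appendix 2 puts its end at study Week 72: "Subjects will receive study drug for dosing until Week 72".

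SAP 3.2 defines the two groups and a pooled one, "all participants who received at least one dose of study assigned B/F/TAF (both immediate and delayed switch to B/F/TAF"). SAP 7.1.5.1 counts an adverse event as treatment-emergent from the first B/F/TAF dose to 30 days after permanent discontinuation. For these events SAP 7.1.6 says: "The number and percentage of participants who experienced at least 1 TEAE will be provided and summarized by SOC, HLT, PT, and treatment group". The same three columns, as numbers and percentages, are used for cardiovascular and hepatic events (7.1.7.2, 7.1.7.3), graded laboratory abnormalities (7.2.2.2) and liver test thresholds (7.2.4). For laboratory abnormalities, "participants will be categorized according to the most severe postbaseline abnormality grade for a given lab test".

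The SAP specifies no person-time rate, no Kaplan-Meier estimate and no incidence table over a common duration. Exposure is summarised in 4.2.1 for the two switch groups; the pooled group is not named there.

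**The concern.** A percentage ever affected rises with time at risk. The columns therefore differ by design even if B/F/TAF carries the same risk in both groups, and the shorter-exposed Delayed Switch column looks safer. The pooled percentage has no common duration. It averages planned exposures of roughly 24 to 72 weeks, with weights set by the 2:1 allocation and by who chose to extend.

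These tables carry the incidence results of the final safety report. A reader comparing columns could take a difference in follow-up for a difference in tolerability. A reader quoting the pooled figure could not say what length of treatment it describes.

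**Working it through.** **Inputs from the documents.** Group sizes are 320 and 160: "Sample sizes of 320 in B/F/TAF FDC and 160 in SBR Group achieve approximately 89% power" (Protocol 8.8). Delayed start is Week 24, main period 48 weeks, extension up to 24 weeks, tail 30 days = 30/7 = 4.29 weeks.

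**The plan's own figure.** The plan gives none for this point. The one computed with these group sizes is the power. The Farrington-Manning normal approximation (4% reference proportion, 6% margin, one-sided 0.025) gives 89.2% against the stated 89%. The point does not depend on it.

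**Step 1: planned exposure (weeks).**

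| | Immediate | Delayed | Ratio | Ratio with tail | Pooled mean |
|---|---|---|---|---|---|
| None extend | 48 | 24 | 0.50 | 28.29/52.29 = 0.54 | (320×48 + 160×24)/480 = 40 |
| All extend | 72 | 48 | 0.67 | 52.29/76.29 = 0.69 | (320×72 + 160×48)/480 = 64 |

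**Step 2: percentage shown when true risk is identical.** With constant hazard h, the percentage over t weeks of treatment is 1 − exp[−h(t + 4.29)]. Event rates and extension uptake are not in the documents, so they are assumed and varied. Everyone is taken to complete planned treatment, with equal extension uptake in both groups.

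Worked case, 5% affected by 24 weeks: h = −ln(0.95)/24 = 0.00214 per week.
- Delayed, no extension: 1 − exp(−0.00214 × 28.29) = 5.9%
- Immediate, no extension: 1 − exp(−0.00214 × 52.29) = 10.6%
- Pooled: (320 × 10.6 + 160 × 5.9)/480 = 9.0%

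**Step 3: range.** The table is indexed by 48-week risk R, with h = −ln(1 − R)/48. The early-onset rows use a Weibull with shape 0.5: 1 − exp[−s(t + 4.29)^0.5], s = −ln(1 − R)/48^0.5. Entries are Immediate % / Delayed % (ratio).

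| Onset | R | None extend | All extend |
|---|---|---|---|
| Constant | 5% | 5.4 / 3.0 (0.55) | 7.8 / 5.4 (0.69) |
| Constant | 30% | 32.2 / 19.0 (0.59) | 43.3 / 32.2 (0.74) |
| Constant | 50% | 53.0 / 33.5 (0.63) | 66.8 / 53.0 (0.79) |
| Constant | 80% | 82.7 / 61.3 (0.74) | 92.3 / 82.7 (0.90) |
| Early | 5% | 5.2 / 3.9 (0.74) | 6.3 / 5.2 (0.83) |
| Early | 80% | 81.4 / 70.9 (0.87) | 86.9 / 81.4 (0.94) |

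Over all cases run (constant-hazard R from 1% to 90%, early-onset R from 5% to 80%), the ratio goes from 0.54 to 0.94. It is below 1 in every one. The pooled percentage for R = 5% with constant hazard moves from 4.6% to 7.0% on extension uptake alone.

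**Step 4: the same data with exposure handled.** Counting only the first 24 weeks of B/F/TAF gives a ratio of 1.00 for any onset pattern, because both groups are planned to have that window. A person-time rate gives 1.00 under a constant hazard: in the worked case both columns read 0.00214 × 52.18 weeks = 11.2 per 100 person-years.

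**The case against.** A reader might infer that Delayed Switch will look half as toxic, or that the columns differ twofold. The documents do not support that in general. Ratios of 0.54 to 0.59 need a constant hazard, no extension and a 48-week risk of at most about 30%. The SAP plans for the extension, and any-TEAE incidence may well be common.

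A reader might also infer that the pooled percentage refers to no defined period. It does have one, set for each participant in SAP 7.1.5.1; what is missing is a common length.

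Nor is exposure ignored. SAP 4.2.1 tabulates it by group, with counts at successive durations up to 72 weeks. Study Day 1 is the first B/F/TAF dose (3.8.1), so by-visit summaries of laboratory tests, liver tests, creatinine, eGFR, proteinuria, weight and vital signs already compare like with like. The lipid sensitivity analysis in 7.2.3 uses Week 72 for one group and Week 48 for the other, so the authors knew of the stagger.

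Finally, the analysis is descriptive, and no hypothesis test or efficacy conclusion depends on these columns. It would be wrong to call the immediate-versus-delayed comparison the trial's only internal safety check, or to say that the objective through Week 48 goes unanswered. The first 24 weeks of SBR data were presented in the Week 24 and Week 48 analyses (SAP 2.2), and the Week 48 SAP is not among the documents.

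All of this stands and limits the point. It does not repair the incidence tables: by-visit means do not give cumulative incidence, and a separate exposure table does not let a reader convert one percentage into another.

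**Conclusion.** The point holds for the incidence tables in SAP 7.1.6, 7.1.7.2, 7.1.7.3, 7.2.2.2 and 7.2.4. Their whole-study percentages are not comparable between immediate and delayed switch, and the pooled percentage mixes durations. Under equal true risk the distortion favours Delayed Switch throughout the cases examined. It is strongest for uncommon events, which may include the serious, discontinuation, cardiovascular and hepatic categories.

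The size rests on assumed event rates, two onset shapes, full completion and equal extension uptake in the two groups; unequal uptake would move the ratio either way. The efficacy results are untouched. This is a worthwhile, inexpensive improvement to the safety reporting.

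**What to change.** For any TEAE, Grade 3-4, related, serious and leading to discontinuation (SAP 7.1.6), and for Grade 3-4 laboratory abnormalities (7.2.2.2), add:

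1. a table limited to the first 24 weeks of B/F/TAF in both groups;
2. exposure-adjusted incidence per 100 person-years for B/F/TAF, Delayed Switch and All B/F/TAF.

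Add All B/F/TAF to the exposure summary in 4.2.1. Footnote all the affected tables, including those in 7.1.7 and 7.2.4, to say that whole-study percentages are not comparable between columns.

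The cost is a few extra tables from first dose, last dose and onset or sample dates already held; no existing table is lost. The rates assume a roughly constant hazard, which the 24-week table offsets. Neither addition removes the selection in Delayed Switch, which contains only participants who completed 24 weeks on their baseline regimen. State that as a remaining limitation.
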